### *Recruitment strategy*

Informational flyers will be posted in various places across OSU's campus including the Food Science and Technology building, Howlett Hall, and Campbell Hall. Additionally, an email will be sent to the student list services including the Food Science and Technology, OSU Nutrition, and Horticulture lists. The study may also be advertised in college and departmental newsletters if needed. Emails and flyers are attached. Interested subjects will be directed to a Qualtrics survey for pre-screening to determine eligibility. Those who meet the study criteria will be contacted by the study coordinator, [name], to begin the informed consent process.

It is expected that subject accrual will be achieved using these methods as they have been successful previously in multiple of our sensory evaluation and clinical studies.

### *Pre-Screening*

Interested participants will be screened through a Qualtrics survey to assess for inclusion and exclusion criteria defined in the previous sections. The Qualtrics survey is attached this application. [name] will review the responses to determine if inclusion and exclusion criteria are met before contacting those eligible.

### *Informed Consent*

Persons who are interested and eligible will be scheduled for a Day -15 visit with a study coordinator at the CRC. On the first visit, participants will begin the informed consent process and all study procedures will be explained. If they agree to participate, subjects will be given a copy of the informed consent form for their records.

### **C. Measurement and Instrumentation**

#### **1. Biological Measures**

The EPA and DHA concentration in multiple blood fractions will be measured including erythrocytes, peripheral blood mononuclear cells (PBMC), platelets, and plasma.

Erythrocyte fatty acids concentration correlates better with intake and reflect longer term intake as compared to plasma . Therefore, the primary objective is to determine if erythrocyte DHA and EPA levels differ after consuming algae oil fortified soymilk versus commercial algae oil capsules daily for four weeks.

A total of 24 mL of blood will be collected at each time point into two Vacutainer EDTA tubes (6 mL each) and 2 CPT tubes (8 mL each).

Blood collected into EDTA tubes will be inverted immediately following collection and then stored on ice until centrifugation (within 1 hour of collection). EDTA tubes will be centrifuged at 1932 x g for 10 minutes at 4°C. The plasma will be extracted and aliquoted into 2 mL tubes. Tubes will be stored on ice after aliquoting. The buffy coat layer will be removed and discarded, and the red blood cells will be extracted. The plasma and RBC aliquots will be stored at -80°C until analysis.

Blood collected in the CPT tubes will be prepared according to the manufacturer's instructions. The tubes will be stored upright and centrifuged within 2 hours of collection. The tubes will be inverted before centrifuging at 1800 x g for 30 minutes at room temperature. A portion of the plasma will be removed from the top of the tube and the cells will be resuspended in PBS buffer to a volume of 15 mL. The tube will be inverted to mix and centrifuged again at 300 x g for 15 minutes. The cells will be washed again with PBS. The remaining pellet will be mixed with 1 mL of PBS and then transferred to 2 mL tubes. After centrifuging again at 300 x g for 5 minutes the supernatant will be aspirated off and the cell pellet will be stored at -80°C until analysis.

Fasting blood samples at each time point will be collected into two Vacutainer tube containing EDTA and immediately stored on ice until centrifugation at 1932 x g for 10 min at 4C. Blood will also be collected in one CPT tube to be used for PBMC samples.

Blood will be separated into three fractions, plasma, PBMC and erythrocytes using previously described methods. Plasma will be stored at -80°C until analysis. PBMC and erythrocytes will be washed with buffer and hemolyzed before being stored at -80°C until analysis.

Fatty acid methyl esters in each fraction will then be separated and analyzed using gas chromatography as described previously. Briefly, lipids from each fraction will be extracted with chloroform and methanol and methylated with hydrochloric acid in methanol. Erythrocyte fatty acids will be extracted and methylated using boron-trifluoride in methanol. Fatty acid methyl esters will then be analyzed using gas chromatography.

Other lipid species and metabolites including cholesterol, eicosanoids, and hormones (leptin, adiponectin, and insulin) may be measured as exploratory endpoints.

## 2. Clinical and Anthropometric Measures

### *Vital Signs*

Pulse, blood pressure, and temperature will be obtained by trained, registered nurses in the CRC using standard clinical methods.

### *Body weight*

Participants will be weighted, wearing light clothing, on a standardized scale.

### *Height*

Height will be measured using a standardized wall-mounted scale.

### *Body mass index*

Body mass index will be calculated using the weight in kg divided by the square of height in meters.

## 3. DHA and EPA Concentration in Ingredients, Beverages, and Capsules

Although the certificates of analysis are provided for the Life's Omega 60 algae oil and the algae oil capsules, we will verify the lipid profile of each to ensure standardization of the two agents.

Fatty acid profiles of algae oil capsule, Life's Omega 60 bulk algae oil (used in beverages), and fortified soymilk will be analyzed. A sterile needle will be used to extract oil from algae oil capsules. Oil from beverages will be extracted using chloroform and methanol. Fatty acids from each oil will be methylated and analyzed using gas chromatography as described previously.

## 4. Food Frequency Questionnaire

To assess diet history, especially habitual consumption of fish and shellfish or fish oil supplements, as well as plant-based milk beverages, a validated food frequency questionnaire will be used.

The Diet History Questionnaire III (DHQIII) from the NIH National Cancer Institute will be used (<https://epi.grants.cancer.gov/dhq3/index.html>). The study coordinators will create a study through the institute site to record and obtain data. The DHQIII includes information on 135 food and beverage items and 26 dietary supplements. The data will be collected for the past month with portion sizes.

Responses will be collected from the participants online when convenient for them during the first week of the study. Login information will be provided at the first clinic visit.

Data from the DHQIII may also be used to assess the Healthy Eating Index of each participant.

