### **First Clinic Visit**

Recruited subjects will meet with the study coordinator at the CRC to begin the informed consent process. The study coordinator, [name], will explain all study procedures as well as explain how to follow the low marine omega-3 diet, fill out daily intake and symptom logs, sensory evaluation forms, and the food frequency questionnaire.

If the subject agrees to participate, they will be given control beverages to consume during the run-in phase and forms including sensory evaluation, food frequency questionnaire, and daily intake and symptom logs. Finally, a preliminary blood sample will be taken from the participant to assess their usual levels of EPA and DHA in blood lipid pools before the washout.

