### **Run-in Phase**

The study will include a 2-week placebo run-in phase where subjects will consume one serving of the control beverage per day with no algae oil. During the run-in the participants will complete a daily intake log, monitoring if and when they consumed the control beverage, as well as complete a log of symptoms, and sensory evaluation on the beverage. These tasks will help familiarize them to the procedures that will be performed during the rest of the study.

Additionally, the two weeks will serve as a washout where they will be instructed to avoid a list of foods and supplements containing EPA and DHA. A food frequency questionnaire will also be used to assess usual intake of fish, shellfish, and plant-based milk beverages and healthy eating index.

Participants will be asked if they would like to receive email reminders detailing daily tasks. If so, study coordinators will send emails reminding the subjects of each daily task including drinking the beverage or taking the pills, filling out the daily dairy and applicable DHQIII or sensory evaluation tasks. Additionally, each participant will be reminded of clinic visits and instructions to come having fasted for 12 hours.

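### The past-month diet questionnaire may be completed up to a week after the study has begun to change the foods it is meant to measure, so habitual marine intake may be understated and plant-milk intake overstated

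*Protocol*

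**What the plan says.** Section III.C.4 (Food Frequency Questionnaire) gives the purpose: "To assess diet history, especially habitual consumption of fish and shellfish or fish oil supplements, as well as plant-based milk beverages". It sets the recall period: "The data will be collected for the past month with portion sizes". On timing it says: "Responses will be collected from the participants online when convenient for them during the first week of the study". It adds: "Login information will be provided at the first clinic visit".

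Under First Clinic Visit, the coordinator is to "explain how to follow the low marine omega-3 diet, fill out daily intake and symptom logs, sensory evaluation forms, and the food frequency questionnaire". Participants who agree to take part then leave with the beverage and the questionnaire together: "they will be given control beverages to consume during the run-in phase and forms including sensory evaluation, food frequency questionnaire".

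Under Run-in Phase, two things happen over the same two weeks. On the beverage: "subjects will consume one serving of the control beverage per day with no algae oil". On diet: "they will be instructed to avoid a list of foods and supplements containing EPA and DHA". That section also places the questionnaire within the run-in, describes it as a measure of usual intake and of the healthy eating index, and lists the DHQIII among the tasks covered by email reminders.

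**The concern.** A questionnaire about the past month describes habitual diet only if the study has not altered diet during that month. Here the login, the dietary restriction and the beverage supply all come from the same visit, and the participant then chooses when in the following week to answer. Each day of delay replaces one day of ordinary diet in the recall window with one day of study diet.

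The foods affected are the ones the questionnaire singles out. Fish, shellfish and omega-3 supplements are withheld, and a plant-milk drink is probably being supplied. The direction of error is therefore predictable, and its size varies between participants because the completion day is left to convenience. Analysis cannot fully undo this, since the ordinary intake displaced by the restriction was never reported.

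At stake are the description of usual marine and plant-milk intake, the Healthy Eating Index if it is derived, and any exploratory analysis of diet. The questionnaire is the only planned measure of usual plant-milk intake, which is useful background when judging how acceptable a soymilk vehicle is.

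**Working it through.** The protocol gives no figure to reproduce; the check is one of timing.

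**Inputs**
- Recall window L: one month (III.C.4), taken as 30 days, with 28 to 31 as the range. The day count is an assumption.
- Completion: any day of the first study week (III.C.4). The login at the first visit and the text of Run-in Phase point to run-in week 1.
- Start of study diet: at or just after the first visit, which Informed Consent places at Day -15. The next visit is day 0 (Study Phase), so a two-week run-in fits Days -14 to -1.
- Beverage: one serving a day (Run-in Phase).
- Assumed: immediate full adherence, habitual intake spread evenly over the month, and accurate recall.

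**Largest overlap, d**
- If Day -15 is day 1 of the first week, its last day is Day -9. With the diet starting on Day -14, Days -14 to -9 give d = 6.
- If the diet starts on the visit day, or the week is counted from Day -14, d = 7.
- A participant who answers at the visit, before starting, has d = 0.

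**Share of the recall window, d/L**

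| d (days) | L = 30 |
|---|---|
| 0 | 0% |
| 1 | 1/30 = 3.3% |
| 3 | 3/30 = 10.0% |
| 6 | 6/30 = 20.0% |
| 7 | 7/30 = 23.3% |

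At d = 7 the range is 7/31 = 22.6% to 7/28 = 25.0%.

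**Fish and shellfish.** Reported rate = habitual rate × (L - d)/L. For an illustrative habit of 2 servings a week:
- d = 6: 2 × 24/30 = 1.60 a week
- d = 7: 2 × 23/30 = 1.53 a week

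**Plant milk.** Someone who never drinks it adds d servings to the month, or 7 × d/30 a week:
- d = 6: 7 × 6/30 = 1.4 a week
- d = 7: 7 × 7/30 = 1.63 a week

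A non-user could thus be recorded as a regular user. For someone who already drinks 7 servings a week, the result depends on whether the study drink replaces the usual one (7.0 a week, no error) or is added to it (7 + 1.63 = 8.63 at d = 7).

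**After the fix.** If the window closes before the diet and beverage start, d = 0 and neither distortion arises.

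**The case against.** The strongest reply is that little depends on this. Data Analysis lists the candidate covariates for the primary outcome, and no questionnaire variable is among them. The Healthy Eating Index and the diet analyses are both worded as optional. Usual EPA and DHA status is measured separately, in blood drawn at the first visit before the washout. All of this stands, and it is why the point is minor.

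A second reply is that the daily logs record when each control beverage was drunk, so study-supplied servings could be separated from habitual plant milk if the completion date is kept. This stands for plant milk. It does not recover the fish, shellfish or supplement intake that the restriction displaced.

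A third is that the coordinator explains the questionnaire in person and could say which month to report. That is possible, but no such instruction is written, and the written timing permits the overlap.

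Some stronger readings are tempting but not supported:
- *Every participant's intake is misstated.* Anyone who answers on the visit day before starting has no overlap, and 23% is a ceiling rather than an expected value.
- *The treatment comparison is biased.* Randomization follows the run-in (Study Phase), so a form completed in run-in week 1 cannot depend on arm.
- *A comparison of the questionnaire with the pre-washout blood sample is undermined.* The protocol plans no such comparison.
- *The control beverage is stated to be soymilk.* The Run-in Phase section says only that it contains no algae oil. Unfortified soymilk is the natural inference, since the study agent is a flavored soymilk and the sensory form rates beany and chocolate attributes.
- *The first week means the first week after randomization, which would make the overlap two to three weeks.* The login at the first visit and the text of Run-in Phase point the other way.

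**Conclusion.** The point holds as a minor flaw in data-collection timing. As written, 0 to about 6-7 of roughly 30 recall days (0% to about 20-23%) may reflect study-imposed diet. Marine intake may be understated and plant-milk intake overstated, unevenly across participants. The upper end requires completion on the last permitted day and prompt, full adherence. The plant-milk half also rests on the control beverage being soymilk. The effect on the Healthy Eating Index cannot be sized from the protocol.

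The primary analysis and the arm comparison are untouched. The harm stops at the description of habitual diet, the optional Healthy Eating Index and the exploratory diet work.

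**What to change.** In section III.C.4, require the DHQIII to be completed at the first clinic visit, after consent and before the dietary restriction and control beverage start. Align the wording under First Clinic Visit and Run-in Phase, including the reminder emails. The questionnaire and login are unchanged; the cost is a slightly longer first visit.

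If completion at home is preferred, keep the first-week window and add one written instruction that the month to report ends the day before the first visit. This costs nothing to run but relies on participants leaving out the most recent days, so it protects the measure less firmly. With either option, keep the completion date so that any remaining overlap can be described.

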## 5. Sensory Evaluation

Sensory evaluation will be recorded during the first day of control beverage consumption for all panelists and during the first and last day of fortified beverage consumption for the algae oil beverage group only. Sensory evaluation will not be performed on the algae oil pills.

The sensory evaluation will include acceptability, just about right, and descriptive attribute tests as well as general impressions. The acceptability tests will include a 9-point hedonic scale from

dislike extremely to like extremely. The categories measured will be overall liking, aroma (smell), flavor (taste), texture (mouthfeel), and appearance.

The JAR tests will measure the level of serving size, chocolate aroma, chocolate flavor, sweetness, and thickness using 5-point scales from “much too little” to “much too much” of an attribute, with the middle being just about right.

The descriptive attribute test will measure their opinion on the intensity of a specific attribute including fishy aroma/flavor, beany aroma/flavor, sweetness, chalkiness, viscosity, and astringency. The scale used will measure intensity from barely detectable to strongest imaginable using a validated labeled magnitude scale.

Finally, there will be questions on general impressions including the sample size of beverages they would consume in a single day, the bottle size, and the flavor.

## **6. Daily Intake and Symptom Journal**

A daily intake journal will be used to assess compliance. Subjects will record if and when they consumed the beverage or pill each day. Additionally, they will record If and when they consumed any of the restricted foods such as fish or shellfish and how much. The final part to the daily log will include recording symptoms such as bad breath, nausea, or bloating.

## **D. Detailed Study Procedures**

### **Study Agent Information**

The study agent is a flavored soymilk beverage fortified with food grade algae oil (Life's Omega 60, DSM, Heerlen, Netherlands). The beverage has been validated by our lab to be physically and oxidatively stable over time and be acceptable in sensory evaluation studies.

The control agent will be a commercial algae oil pill (Swanson Plant Based Omega-3) containing the same Life's Omega 60 oil. These supplements are produced in an NSF International registered facility utilizing good manufacturing practices. Additionally, their purity and potency are assessed by an independent third-party laboratory.

<https://info.nsf.org/Certified/455GMP/Lists.aspx?Company=C0054895&Standard=455-2GMP>

<https://info.nsf.org/Certified/GMP/Lists.aspx?Company=C0054895&Program=DIETSUPP>

All plant milk samples will be prepared in the FDA inspected Food Processing Pilot Plant (Howlett Hall) or the Dairy Processing Pilot Plant (Parker Food Science and Tech Building) using Good Manufacturing Practices. All products prepared for human consumption in this project contain wholesome food ingredients and Generally Recognized as Safe food additives. All ingredients will be food grade.

Algae oil (0.4%) will be mixed with high oleic sunflower oil, liquid lecithin, and butylated hydroxy toluene (BHT) and stirred on a hot plate set to 500 rpm and 50°C until lecithin is evenly dispersed (about 10 minutes). The water phase will be prepared by mixing 0.1% gellan gum and 1% polysorbate 80 into water using a hot plate set to 1000 rpm and 85°C. To prepare the base emulsions, 21%

Concentrated soymilk base or soymilk powder will be combined with water (to manufacturer's instructions) sugar (2%), salt (0.1%), emulsion base (10%), and cocoa powder (2-3%) before

being homogenized, and heat treated (136°C for 4 seconds). The plant milks will be cooled and bottled in aseptic hood. All samples will be refrigerated after bottling.

Fresh soymilk will be prepared less than one week before the first week of the study and will be utilized throughout the duration of the study. Prior to this study, a confirmatory shelf-life study will be done to ensure that the storage time does not influence the fortified soymilk sensory perception. If needed, fresh samples can be prepared weekly or biweekly to ensure acceptability.

### **First Clinic Visit**

Recruited subjects will meet with the study coordinator at the CRC to begin the informed consent process. The study coordinator, [name], will explain all study procedures as well as explain how to follow the low marine omega-3 diet, fill out daily intake and symptom logs, sensory evaluation forms, and the food frequency questionnaire.

If the subject agrees to participate, they will be given control beverages to consume during the run-in phase and forms including sensory evaluation, food frequency questionnaire, and daily intake and symptom logs. Finally, a preliminary blood sample will be taken from the participant to assess their usual levels of EPA and DHA in blood lipid pools before the washout.

### **Run-in Phase**

The study will include a 2-week placebo run-in phase where subjects will consume one serving of the control beverage per day with no algae oil. During the run-in the participants will complete a daily intake log, monitoring if and when they consumed the control beverage, as well as complete a log of symptoms, and sensory evaluation on the beverage. These tasks will help familiarize them to the procedures that will be performed during the rest of the study.

Additionally, the two weeks will serve as a washout where they will be instructed to avoid a list of foods and supplements containing EPA and DHA. A food frequency questionnaire will also be used to assess usual intake of fish, shellfish, and plant-based milk beverages and healthy eating index.

Participants will be asked if they would like to receive email reminders detailing daily tasks. If so, study coordinators will send emails reminding the subjects of each daily task including drinking the beverage or taking the pills, filling out the daily dairy and applicable DHQIII or sensory evaluation tasks. Additionally, each participant will be reminded of clinic visits and instructions to come having fasted for 12 hours.

### **Study Phase**

After the run-in, the participants will then be randomized to the beverage or pill group. During the study phase, there will be three clinic visits to the Cancer Research Center. The visits will occur on day 0, 14, and 29. At each visit, blood will be drawn.

Additionally on days 1 and 28, they will perform a sensory evaluation on the beverage using provided forms. The second sensory evaluation will be used to determine if long-term consumption of the beverage impacted its perception.

Over the course of the 28 days, participants will complete daily intake and symptom logs to ensure compliance to the low marine omega-3 diet and study intervention as well as monitor adverse effects.

To ensure compliance during the study, participants will be asked to return empty beverage or pill containers and any that were not consumed. One to three extra beverages or pills will be given to estimate how many were consumed.

Participants will again be asked if they would like to receive email reminders detailing daily tasks.

